### **Secondary:**

- i. Improvements in calf muscle function as measured by venous plethysmography (ejection fraction, VFR, PDR T90, EDV T90).
- ii. Improved quality of function : Godin questionnaire (validated questionnaires to measure physical activity), VEINES-QOL (generic physical quality of life questionnaire) and Villalta Score (to assess Post-Thrombotic Syndrome)
- iii. Analyze whether shear wave elastography will provide a more accurate and reliable method to assess the age of thrombosis and better quantification of thrombosis resolution.

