To further reduce the VTE burden, better treatments are needed to resolve VTE other than anticoagulation alone. The largest randomized trial to date is the Pulmonary Embolism International Thrombolysis (PEITHO) trial, and resulted in 1,006 patients with acute sub-massive PE-defined as echo evidence of RV dysfunction or positive troponin-to receive anticoagulation with heparin plus tenecteplase or placebo. There was significantly (2.6% vs. 5.6%;  $P=0.015$ ) lower death or hemodynamic collapse within 7 days and increased rates of intracranial hemorrhage (2.4% vs 0.2%;  $P=0.003$ ) and major bleeding in the thrombolytic group. The Seattle II study was a prospective, single-arm multicenter trial of ultrasound facilitated, low-dose fibrinolysis for acute massive and sub-massive PE. There was a 25% decrease in CT-measured RV/LV ratio over 48 hours, 0% intracranial bleeding, 2% in-hospital death, and 2.7% 30 day mortality due to catheter-directed low-dose fibrinolysis. The rationale for the Seattle II study was to use catheter-directed-low dose fibrinolysis as a disruption device to help dissolve clot. However, there is limited data on the use of vascular boot and warming plus standard anticoagulation in the long term management of patients with DVT and/or PE and its effect on the development of PTS. Warming of the lower extremity enhances blood flow in the treatment of superficial vein thrombosis.

Currently the standard method for diagnosing and evaluating DVT is by 2-D ultrasound with compression and visualization of the vein. Due to the lack of accurate age determination method of DVT, about 30% of DVTs are wrongly staged by using common diagnostic modalities and therefore this leads to therapeutic dilemmas. As thrombus undergoes a stiffening process, the elasticity of the thrombus may serve as a predictor

for the staging of blood clots. Ultrasound elastography is a noninvasive technique to measure tissue stiffness and is a potential technique to determine the age of DVT. When DVT changes due to resolution the function and viscoelastic properties also change. We propose the use of a quantitative, noninvasive method call Shear wave Dispersion ultrasound vibrometry, to measure the viscoelastic properties of the vein.

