**Inclusion Criteria**

1. Age ≥18
2. Able to tolerate wearing a vascular boot, if randomized to this group.
3. Diagnosis of acute DVT±PE (within 24 - 48 hours) and received approximately 24 hours of anticoagulation prior to starting the study.

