#### Baseline studies will include:

- (1) Venous plethysmography: (ejection fraction, VFR, PDR T90, EDV T90, MV, F1.0).
- (2) Lower Extremity Ultrasound: DVT (thrombus) evaluation with 2-D ultrasonography (standard) and shear wave elastography (done within 1 day of baseline clinical ultrasonography).
- (3) Other relevant clinical information (such as height, weight, BMI, bilateral calf circumference, edema, leg pain, ulcerations, previous LE surgery, use of compression stockings, and any current set exercise program). Demographical data, common vascular risk factors (including tobacco use, coronary and peripheral arterial occlusive disease, diabetes, hypercholesterolemia, and hypertension) and the treatment information, will be obtained from chart review via ACE database and Synthesis. All data will be entered and stored in RedCap research tool.
- (4) Anatomic distribution of thrombi at initial examination will be documented as single segment and/or multi-segment(s) involved. The segments will be label as: external iliac vein (EIV), only if clot extends above the common femoral vein; common femoral vein (CFV); femoral vein (FV) (upper, middle, lower); deep femoral vein (DFV); popliteal vein (PV); posterior tibial vein (PTV); gastrocnemius (G-calf); peroneal vein-calf (PV-calf); soleal vein-calf (SV-calf) (see Table 1).

Table 1.0

Site	Anatomic Distribution of Thrombi			
	Initial	3 days	10 days	3 months
Single Segments				
External Iliac (EIV); if evaluated				
Common femoral (CFV)				
Femoral- Upper (FV)				
Femoral - Middle				

Femoral - Lower				
Deep Femoral (DFV)				
Popliteal (PV)				
Posterior Tibial (PT-calf)				
Gastrocnemius (G-calf)				
Peroneal (P-calf)				
Soleal (S-calf)				
Total				
Multisegment				
EIV- CFV				
EIV- CFV-FV				
EIV- CFV-FV-PV				
EIV- CFV-FV-PV-calf				
CFV-FV				
CFV-FV-PV				
CFV-FV-PV-calf				
FV-PV				
FV-PV-calf				
Total				

Patient will then be randomized to vascular boot plus standard anticoagulation program or standard anticoagulation using the randomizer built into RedCap.

**Standard of Care (SOC) Group (no vascular boot utilized)**: Patients will receive standard anticoagulation (determined at discretion of the treating provider), baseline studies, and follow up at the end of treatment (3months).

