**Follow up data (SOC and VB Groups) include:**

- (1) Ultrasound of the leg with DVT and leg circumference measurement at 3 days, 10 days, and 3 months. Ultrasound data will include data on thrombus resolution, such as size and recanalization present.
- (2) Venous plethysmography at 3 months.
- (3) Study Questionnaires:
  - a. Godin questionnaire (validated questionnaires to measure physical activity)
  - b. VEINES-QOL (generic physical quality of life questionnaire)
  - c. Villalta Score (to assess Post-Thrombotic Syndrome)

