**Ultrasound Measurements and Criteria:**

The criteria for complete occlusion (occlusive) were absence of flow with distal augmentation and incompressibility of the vein. Minimal clot will be defined by wall thickening, webbing, etc. Partial recanalization will be defined by >50% or <50% normal or diminished flow with distal augmentation and partial incompressibility of the vein. Complete recanalization (resolved or no clot) will be defined by spontaneous phasic flow and a completely compressible vein and no residual clot (see Table 2).

Table 2.0

Site	No Residual Clot	Minimal Clot (wall thickening, webbing, etc)	Recanalized >50%	Recanalized <50%	Near Occlusive	No Change	Worse Or Extension
External Iliac (EIV); if evaluated							

Common femoral (CFV)							
Femoral- Upper (FV)							
Femoral - Middle							
Femoral - Lower							
Deep femoral (DFV)							
Popliteal (PV)							
Posterior tibial (PT-calf)							
Gastrocnemius (G-calf)							
Peroneal (P-calf)							
Soleal (S-calf)							
Total							

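### Endpoint iii asks whether elastography is more accurate for clot age, but no age reading from standard ultrasound is defined and no symptom-onset date is listed, so superiority for age cannot be tested as planned

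*Combined protocol and SAP*

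**What the plan says.** Endpoint iii (Endpoints, Secondary) reads "Analyze whether shear wave elastography will provide a more accurate and reliable method to assess the age of thrombosis" and then adds better quantification of resolution. Secondary Objective 6 repeats it, and the Study Rationale lists it among the results the study expects to demonstrate. The Background identifies 2-D compression ultrasound as the current standard and states that "about 30% of DVTs are wrongly staged by using common diagnostic modalities".

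The data to be collected are as follows.

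- **Baseline imaging** (Baseline studies, item 2): "DVT (thrombus) evaluation with 2-D ultrasonography (standard) and shear wave elastography (done within 1 day of baseline clinical ultrasonography". Table 1 records which vein segments are involved.
- **Follow-up imaging** (Follow up data, item 1): "Ultrasound data will include data on thrombus resolution, such as size and recanalization present".
- **2-D grading** (Ultrasound Measurements and Criteria, Table 2): seven categories of residual clot or change, with definitions such as "Minimal clot will be defined by wall thickening, webbing, etc" and "Partial recanalization will be defined by >50% or <50% normal or diminished flow with distal augmentation and partial incompressibility of the vein".
- **Clinical data** (Baseline studies, item 3): "Other relevant clinical information (such as height, weight, BMI, bilateral calf circumference, edema, leg pain, ulcerations, previous LE surgery", followed by further items. Neither onset date nor symptom duration is among them.
- **Entry** (Inclusion Criteria, item 3): "Diagnosis of acute DVT±PE (within 24 - 48 hours", with about a day of anticoagulation already given.
- **Elastography** (Study Procedure): research scans on days 0, 3, 10 and 90, with windows. The only named control is the opposite leg, if free of DVT. Images are stored and measured offline by one blinded observer.
- **Analysis** (Data Analysis Plan): elastography is to be assessed for validity. No reference standard, accuracy measure or agreement statistic is named.

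**The concern.** A claim of greater accuracy has three parts: a reading from the new method, a reading of the same quantity from the rival, and a reference value for both. Here the quantity is clot age. The rival's age reading is not defined, and the reference is left to whatever dates happen to be available.

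The reference is weakest at presentation, which is where the Background and Study Rationale place the clinical problem of clots of uncertain age. At that visit every patient has been diagnosed within a day or two. At later visits, recorded age rises together with days on anticoagulation and with resolution of the clot. A change in stiffness across visits could reflect any of these, and it would say nothing about how well 2-D ultrasound judges age.

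**Working it through.** The plan has no figure to reproduce: the 30 patients are stated not to come from a calculation. The check is first a reading of the plan, then a simple illustration of how good the available age reference is.

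**Step 1. What the comparison needs and what the plan supplies**

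| Needed | Supplied |
|---|---|
| Elastography measure | Shear-wave measurements at each research scan |
| Age reading from 2-D ultrasound | None; location, size, recanalization and change only |
| Reference age | Diagnosis date (the identifier table marks dates as recorded and gives diagnosis as an example); onset not listed |
| Accuracy or agreement statistic | None named |

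The opposite leg has no clot, so it cannot serve as a reference for clot age. The number of paired age readings specified is 0.

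**Step 2. How much of true age the calendar captures**

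Take true age = onset-to-diagnosis delay + days since diagnosis, with the delay independent of scan day. Use the nominal scan days as days since diagnosis and weight scans equally. Then

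share captured = Var(scan days) / [Var(scan days) + SD_delay²].

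- Days 0, 3, 10, 90: mean 25.75; variance = (663.06 + 517.56 + 248.06 + 4128.06)/4 = 1389.19.
- Days 0, 3, 10: mean 4.33; variance = (18.78 + 1.78 + 32.11)/3 = 17.56.
- Day 0 alone: variance 0.

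The documents give no SD for the delay, so a range is assumed.

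| Assumed SD of delay (days) | Four scans | First three scans | Day 0 only |
|---|---|---|---|
| 1 | 0.999 | 0.946 | 0 |
| 3 | 0.994 | 0.661 | 0 |
| 7 | 0.966 | 0.264 | 0 |
| 14 | 0.876 | 0.082 | 0 |

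For example, with an SD of 7 days and the first three scans: 17.56/(17.56 + 49) = 0.264.

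**Step 3. How far recorded age can be told apart from visit**

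The windows in Study Procedure give day 3 a span of 1 to 8 (3 − 2, 3 + 5), day 10 a span of 5 to 15, and day 90 a span of 76 to 104. The day-3 and day-10 windows overlap, so recorded age is not identical to visit number. Between day 15 and day 76 there are no planned scans. The high four-scan shares come mostly from the distance between the last visit and the first three, and that is also the difference between short and long treatment.

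**Step 4. What a retrospective 2-D age reading could supply**

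30 patients × 4 scans = 120 stored image sets. This is an upper bound, because a resolved clot cannot be aged. The Background cites complete resolution in more than 40% of segments by 3 months.

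**The case against.** The strongest defence is that a reference for age does exist. Diagnosis dates are recorded, entry is tied to recent diagnosis, previous DVT or PE is excluded, and scan days are fixed. Stiffness can therefore be related to time since diagnosis within each patient, and Step 2 shows this is a good proxy over the full 90 days. This stands. A reader might infer that elastography has nothing at all to be compared with; the documents do not support that.

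Three other stronger readings also fail.

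- **That onset dates will not be recorded.** The baseline list is open-ended and chart abstraction is described in general terms. The documents support only that onset is not listed, so nothing assures it.
- **That the whole endpoint is untestable.** For quantifying resolution, the Table 2 grades are a usable 2-D comparator.
- **That the 30% mis-staging figure sizes the problem.** If 2-D accuracy were 70%, its 95% half-width in 30 patients would be 1.96 × √(0.7 × 0.3/30) = 0.164. That is the precision of one proportion, not of a difference between two methods, and the cited figure concerns common modalities rather than 2-D ultrasound specifically.

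It is also fair to say that this is a pilot, and that the Statistical Information note excuses pilots from power analyses and endpoints. That answers a complaint about sample size. It does not supply a comparator for a comparative aim that the protocol chose to state. None of these defences provides the missing 2-D age reading.

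**Conclusion.** The point holds for clot age only. As planned, there are 0 paired age readings, so superiority of elastography over 2-D ultrasound for age cannot be tested. Time since diagnosis is the only assured reference. It carries no information on differences in age at day 0. Over the first three scans it captures about 66%, 26% or 8% of age variance if the delay SD is 3, 7 or 14 days, and over all four scans 88% or more. These shares rest on the assumed SDs, on independence of delay and scan day, and on nominal scan days. The absence of a 2-D age reading rests on no assumption.

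A reader might infer that the trial will report a stiffness trend as proof of greater accuracy. The documents do not say so; the Data Analysis Plan speaks only of validity and of whether thrombus can be quantified. The supportable statement is that the data could describe stiffness by time since diagnosis, but could not rank the two methods for age. This is a moderate point on a secondary endpoint and is cheap to settle before data are collected.

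**What to change.** Either of two changes settles it.

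**Option A: make the age comparison possible.**

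- Add symptom-onset date to the baseline data, asked at enrolment.
- Have the existing blinded observer assign an age class (for example acute, subacute or chronic) from the stored 2-D images that still show clot. Images should be read in random order, masked to visit, arm and elastography.
- Compare that class and shear-wave stiffness against days since onset, dichotomised at a cut-point stated in advance, by the paired difference in AUC with a bootstrap that resamples patients. Alternatively, use rank correlation of each method with continuous age. A cut-point in the gap between day 15 and day 76 would largely just separate the last visit from the others, so the choice should be justified.
- Report the result as exploratory. State that age is confounded with days on treatment and that 120 image sets is a ceiling.

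**Option B: state a more modest aim.** Reword only the age part of endpoint iii, and the matching objective and rationale text, to: *describe change in clot stiffness by days since diagnosis*. Drop the claim of greater accuracy for age. Keep the comparison of elastography with Table 2 grades for thrombus resolution.

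Option A costs one date field and a few minutes of reading per stored image set, with no new scans or staff. Option B costs a short rewording and a less ambitious claim.
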